Education of Municipality-based Physiotherapists in Managing Chronic Low Back Pain - an Observational Study

Date

March 20th 2023

Ethical committee reference number

S-20222000 - 156

Objective

To investigate potential changes in patient outcomes following an educational intervention aimed at upskilling physiotherapists in individualized bio-psycho-social management of patients with disabling low back pain (dLBP) in municipality rehabilitation settings. Focus will both be on changes in patient reported outcomes as well as changes in clinician behavior. Likewise, the feasibility of implementing such changes within municipality settings will be evaluated

Method

Design

A prospective, observational case-control study

Participants

Patients with dLBP referred to municipality-based rehabilitation from the Spine Centre of Southern Denmark. Eligibility is determined on the following criteria:

Inclusion Criteria:

- Referred to municipality rehabilitation from the Spine Centre of Southern Denmark
- Over 18-65 years
- Speaks and comprehends Danish
- A score over 40 on the Örebro Musculoskeletal Pain Questionnaire
- Low back pain as dominating cause for referral
- Can receive digital mail in E-boks (electronic communication platform)

Exclusion Criteria:

- A current diagnosis of psychiatric illness that precludes participation in rehabilitation
- a neurologic disorder or other disease that may affect the ability to participate in a municipality-based rehabilitation program
- neurological deficits related with radiographically confirmed lumbar spinal stenosis or radicular pain correlating with the clinical presentation
- Recent (within 6 months) history of a stabilizing operation of the low back

Procedures

Data collection:

All demographic information will be collected at baseline. This includes age, gender, weight, smoking (yes/no), diagnosis, duration of symptoms, job status (Working Yes/No. If Yes: normal capacity or reduced capacity because of back pain. If No: Full-time sick-listed because of back pain or sick-listed due to other reasons) if early retirement: due to back pain?), highest completed education beyond elementary school)

Primary Outcome

Roland Morris Disability Questionnaire 3 months after entering the study

Secondary outcomes

- Pain intensity (lower back and leg) 3 months after entering the study with a numeric rating scale (NRS:0-10)
- Örebro Musculoskeletal Pain Questionnaire 3 months after entering the study

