- Self-perceived ability to work (NRS: 0-10) 3 months after entering the study
- Patient satisfaction, 7-point Likert scale 3 months after entering the study

Other Pre-specified Outcome Measures:

- Checklist to determine the competency of clinicians immediately after study completion
- Barriers and facilitators for implementing new knowledge in clinical practice – qualitative interview

3 month follow-up

- Roland Morris Disability Questionnaire at 3 months after discharge
- Pain intensity (lower back and leg) with a numeric rating scale (NRS:0-10)
- Self-perceived ability to work (NRS: 0-10)
- Patient Assessment of Transitions in Healthcare (PATH)
- Patient satisfaction, 7-point Likert scale

Other Pre-specified Outcome Measures:

- Checklist to determine the competency of clinicians and to assess interrater reliability between clinical supervisors
- Barriers and facilitators for implementing new knowledge in clinical practice – qualitative interview

Schedule of procedures and assessments (for a schematic overview, see fig. 1)

1. All participating physiotherapists (N=25) will recruit eligible patients (N=4 each, total N=100) who are asked to fill out project-specific questionnaires (see *procedures*) at the start and at the end of the rehabilitation program.
2. The participating physiotherapists will undergo a 13-day educational intervention (see description below under *intervention*) focusing on management of low back pain within an individualized multidimensional framework.
3. Point 1 is repeated on an additional 100 patients who undergo rehabilitation after the physiotherapists have completed the course
4. Participating physiotherapists will be evaluated on the background of a competency checklist which is scored by clinical supervisors connected to the study. The checklist will be scored after watching a video recording of a patient consultation performed by the physiotherapist in focus. The checklist covers 6 domains: Subjective and objective assessment, cognitive-functional therapy intervention, style of communication, patient's unhelpful pain behavior, and an overall assessment
5. Physiotherapists who demonstrate high and low competency (as determined by the evaluation of competency, point 4) are invited to participate in a semi-structured interview. The interview will explore the physiotherapists' experience of changes in management (if

any) after the educational intervention. This includes challenges, barriers and facilitating factors.

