Statistical analysis will be performed using the appropriate statistical method according to the specific aims investigated. All demographic variables will be presented as means (\pm standard deviations), median [Interquartile range], or ratio (%) depending on type and distribution of data. All primary and secondary outcomes will be analysed using paired tests (parametric or non-parametric based on normality), comparing baseline data and data 3 months after study start.

The sample size calculation is based on the previous findings of Ussing et al (2020)¹ which included a similar population and was conducted in a specialist spine clinic in a secondary setting. Based on these findings, we expect to find a 30% group difference in disability in favor of the post-education group. With a mean of 36 (SD 18) pre-intervention and 28 (SD 18) post-intervention, we expect that N=100 participants in each group will be sufficient to achieve an alpha level of 0.05 with a 0.8 power assuming a 10-15% dropout-out rate.

Ethical considerations

Participation in the study does not imply any risks for the patients. All study related procedures are either clinically indicated or do not come with any risk or harm. The patient needs to spend a little extra time filling out project-specific questionnaires as compared with standard care. The overall burden of participating is outweighed by the potential gain. This study is conducted in full conformance with the principles of the Helsinki Declaration. However, the project falls outside the scope of the ethical committee (regional and national) in Denmark as it falls under quality assurance.

¹ <https://pubmed.ncbi.nlm.nih.gov/32221554/>

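### The blanket paired test does not fit patient satisfaction: no baseline rating is described, and a rating of care received would have none, so this secondary outcome lacks a workable analysis.

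*Combined protocol and SAP*

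**What the plan says.** All references are to the combined protocol and SAP.

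- **Statistics** gives one rule for every declared outcome: "All primary and secondary outcomes will be analysed using paired tests", parametric or not according to normality, "comparing baseline data and data 3 months after study start". No outcome is excepted. The section opens with a general statement that suitable methods will be chosen for each aim, but names no alternative for satisfaction.
- **Secondary outcomes** ends with "Patient satisfaction, 7-point Likert scale 3 months after entering the study". The text does not say what the patient is asked to be satisfied with.
- **3 month follow-up** lists satisfaction again, in a list whose disability entry is timed from discharge rather than from entry.
- **Procedures, Data collection** says "All demographic information will be collected at baseline" and itemises no outcome measure at that visit.
- **Schedule of procedures and assessments** has patients "asked to fill out project-specific questionnaires" "at the start and at the end of the rehabilitation program", without saying which items belong to which time. It then adds a second group: "Point 1 is repeated on an additional 100 patients who undergo rehabilitation after the physiotherapists have completed the course".

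**The concern.** A paired test needs the same quantity measured twice in the same patient. For disability, pain, the Örebro score and work ability this is natural, because each describes a state the patient is already in on arrival. Satisfaction in its usual sense is a judgement on care that has been delivered, and at entry the rehabilitation has not begun.

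If the item is of that kind, following the plan literally produces no result for a declared secondary outcome. The analyst would then have to choose a method later, possibly with the data in view. The informative contrast for satisfaction is between patients treated before and after the physiotherapists' education, and the plan does not assign that contrast to it.

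**Working it through.** The plan gives no figure for satisfaction, so there is none to reproduce. The check is mainly a comparison of the sections.

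**Step 1: does the rule cover satisfaction?** Yes. The Statistics rule covers all primary and secondary outcomes, and satisfaction is one of four bullets under Secondary outcomes (pain intensity, Örebro, work ability, satisfaction).

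**Step 2: is a baseline value described?** No. Two cautions apply:
- The 3-month-only wording is not peculiar to satisfaction. The primary is worded the same way: "Roland Morris Disability Questionnaire 3 months after entering the study". That wording alone therefore cannot show that a baseline is absent.
- The start-of-programme questionnaire is not itemised, so it neither includes nor excludes a satisfaction item.

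For Örebro, an entry score is implied independently, because a score over 40 is an inclusion criterion. Nothing comparable implies an entry score for satisfaction.

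**Step 3: what follows under each possible meaning of the item?**

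| What the item rates | Value at entry | Paired test |
|---|---|---|
| The rehabilitation received (usual meaning) | None that is meaningful | Does not apply |
| Care so far; at entry, care at the referring Spine Centre | Possible | Can be computed, but compares ratings of two different services |
| Present symptoms or condition | Possible | Applies, if the item is asked at entry |

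Only the third meaning supports the planned test, and the document neither states that meaning nor shows that the item is asked at entry.

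**Step 4: would a general move to a between-cohort analysis solve it?** Only if it used the 3-month values. A change score, or adjustment for the outcome's own baseline, would work for the other three secondary outcomes and for disability. It would not work for an outcome without a baseline.

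**Step 5: what could a cohort comparison of the 3-month rating detect?** Inputs from Statistics: 100 patients per cohort, 10–15% dropout, alpha 0.05 and power 0.8. Two-sided testing is assumed, as the plan does not state sidedness.

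- Evaluable per cohort: 100 × 0.85 = 85 to 100 × 0.90 = 90, so total N = 170 to 180.
- Rank-sum formula with equal groups: p = 0.5 + √[(1.96 + 0.8416)² / (3N)], where p is the probability that a random patient from one cohort rates higher than one from the other.
- (1.96 + 0.8416)² = 7.849.
- N = 170: 0.5 + √(7.849/510) = 0.5 + 0.124 = 0.624.
- N = 180: 0.5 + √(7.849/540) = 0.5 + 0.121 = 0.621.

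The formula treats patients as independent and ignores ties. The study has 25 physiotherapists with 4 patients each per phase, the same physiotherapists in both phases, and only seven response categories. The figure of about 0.62 is therefore indicative. It describes what the proposed comparison could detect and does not measure the defect.

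**The case against.** The strongest reply is that the document never says satisfaction lacks a baseline value. A reader might infer that the paired test is impossible and that none of the up to 200 patients would supply a pair. The documents do not support this as fact: every outcome shares the 3-month wording, the start questionnaire is not itemised, and the satisfaction construct is undefined. If the argument rested on timing alone, it would remove the primary outcome's pair as well. This part of the reply stands.

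A second reply is that the general opening of Statistics leaves room for another method. It does not pre-specify one, and the specific sentence that follows covers all outcomes and names the test and the time points.

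A third is that the plan states no between-cohort test for any outcome, so the matter belongs to that wider question. The overlap is real. A wider correction built on follow-up values would also cover satisfaction, but one built on change or own-baseline adjustment would not, so a separate sentence is still needed.

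A reader might also extend the point to the care-transitions questionnaire (PATH). It appears only under 3 month follow-up and not among the declared secondary outcomes, so the paired rule does not clearly reach it.

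Finally, a particular ordinal model and covariate set is one reasonable choice among several.

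**Conclusion.** The point holds in a limited form. The plan requires a paired baseline-to-3-month test for satisfaction without describing a baseline measurement or defining the item. If the item rates the rehabilitation received, the test does not apply and the outcome has no workable analysis. That conclusion rests on the usual meaning of patient satisfaction, which the document does not confirm. If the item instead rates present condition and is asked at entry, the paired test can be run and the remaining defect is missing definition.

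The size is modest: one of four listed secondary outcomes, with no effect on the primary. It should still be corrected before analysis, because each reading requires at least a definition of the item.

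**What to change.** 1. State what the satisfaction item rates and when it is asked, and list the contents of the start and end questionnaires. Say whether the rating to be analysed is the one timed from study entry or the one in the follow-up list.
2. Exempt satisfaction from the paired rule.
3. Compare the rating at 3 months after study entry between the pre-education and post-education cohorts with an ordinal method that accounts for clustering by physiotherapist. A proportional-odds model is one option and a rank-based comparison is another. If proportional odds is chosen, name a check of the assumption and a fallback. Adjustment for baseline disability and baseline Örebro score is optional.
4. Report the effect estimate with its 95% CI and the distribution over the seven categories in each cohort.

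The comparison uses the two cohorts and the 3-month ratings already planned. The cost is a paragraph of wording and a little more analysis, with no additional data.

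### The primary test is chosen after a normality check and no effect estimate is named; neither branch estimates the group difference the study was sized on

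*Combined protocol and SAP*

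**What the plan says.** The Statistics section has one sentence on how outcomes are tested: every primary and secondary outcome gets "paired tests (parametric or non-parametric based on normality", and the contrast is given as "comparing baseline data and data 3 months after study start". The section does not say:

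- which tests are meant;
- how normality is judged, or on which variable (raw scores or within-patient changes);
- which estimate and confidence interval are reported.

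The sentence covers the primary outcome, "Roland Morris Disability Questionnaire 3 months after entering the study".

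The sample size paragraph in the same section uses a different comparison: "we expect to find a 30% group difference in disability in favor of the post-education group". Its inputs are "With a mean of 36 (SD 18) pre-intervention and 28 (SD 18) post-intervention", and it concludes that "N=100 participants in each group will be sufficient". The two groups are different people. Under the schedule of procedures, 25 physiotherapists recruit 4 patients each before the course, and then "Point 1 is repeated on an additional 100 patients who undergo rehabilitation after the physiotherapists have completed the course".

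**The concern.** A paired t-test concerns the mean change. A rank-based paired test such as the signed-rank test concerns the pseudo-median of the change, and the two coincide only when changes are symmetric. If the observed distribution picks the test, it also picks the quantity reported. Skewed changes are one reason to leave the t-test, and they also break the symmetry that the signed-rank test needs, so the fallback is not a clean repair. Because the rule is unstated, two analysts could follow the plan and report different things, and pain, work ability and disability could each be handled differently.

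The second part is larger. The study asks whether outcomes are better after the physiotherapists are trained, and it is sized on that difference. A paired comparison of baseline with 3 months describes change over a course of rehabilitation. It does not compare the two cohorts, whichever branch is taken.

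**Working it through.** **1. What the sample size supports.** The inputs, from the Statistics section, are means 36 and 28 (difference 8), SD 18, alpha 0.05 and power 0.80. A two-sided test is assumed because the plan does not state sidedness. For two independent means:

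n per group = 2 × (1.960 + 0.842)² × 18² / 8² = 2 × 7.849 × 324 / 64 = 79.5, so 80 (81 with the t distribution).

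- 10% dropout: 80 / 0.90 = 88.9, so 89.
- 15% dropout: 80 / 0.85 = 94.1, so 95.

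The stated 100 per group is not reproduced exactly, but it is on the safe side. Enrolling 100 leaves 90 or 85 evaluable.

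| Evaluable per group | SE = 18 × √(2/n) | 8 / SE | Power, normal | Power, t |
|---|---|---|---|---|
| 90 | 2.683 | 2.981 | 0.846 | 0.843 |
| 85 | 2.761 | 2.897 | 0.826 | 0.821 |

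**2. Whether the 36 and 28 could be a within-patient change.** The SD of a change is 18 × √(2(1 − r)), where r is the baseline-to-follow-up correlation. The plan gives no r. At an assumed r = 0.5 it is 18, and the number needed is 7.849 × 324 / 64 = 39.7, so 40 patients in all. With 85 pairs, power would be 0.817 at r = 0, 0.928 at 0.3, 0.982 at 0.5 and 0.999 at 0.7. A requirement of 100 in each of two groups, worded as a group difference favouring the post-education patients, fits a between-cohort comparison and not a paired one.

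**3. The two contrasts side by side.**

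| | Sizing | Planned test |
|---|---|---|
| Compared | Pre-education patients with post-education patients | Baseline with 3 months |
| Patients | Different people | Same people |
| Quantity | Difference in means, 8 points | Mean change or rank-based shift, decided by the data |

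The paired contrast loses the sized difference before normality is considered.

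**4. How often the switch would change the primary result.** The plan names no normality test, score scale or correlation. These are therefore assumptions: Shapiro-Wilk at 0.05 on the within-patient change, a 24-step score rescaled to 0–100, means 36 and 28, SD 18, correlation 0.3 to 0.7, and 85 to 90 patients in the cohort tested.

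- At 85 patients, normality of the disability change is rejected in 7% to 22% of trials.
- The paired t-test and signed-rank test disagree on significance in 0.1% to 2.5% of all trials.
- Rejection together with disagreement occurs in at most 0.2% to 0.6% of trials, depending on the assumed shape. With a true change of 4 points it stays below 2%, and with no change below 1%.
- Both tests keep a type I error near 0.05 when there is no change.

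**5. How far the reported quantity can move.** This takes an assumed skewed change with mean 8 and SD 18 (gamma, shape 4); nothing in the documents supports that shape in particular. Shapiro-Wilk rejects in about 92% of samples of 85. In one draw of 4,000 values, the mean was 8.1 and the signed-rank pseudo-median 6.6, a gap of 1.5 points on a planned effect of 8.

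**The case against.** **The effect on the primary conclusion is negligible.** This stands for significance, on the assumptions in step 4. The 1.5-point gap in step 5 needs a marked skew that the documents do not imply.

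**The plan names no formal test or cut-off, so the rule is being over-read.** It is right that Shapiro-Wilk and the signed-rank test are assumptions here. But an unstated rule leaves more discretion, not less.

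**A rank analysis need not lose the points scale.** True: a Hodges-Lehmann estimate with a confidence interval is in points. The plan specifies neither that nor an estimate for the parametric branch, so the missing estimate is a gap in both.

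**The remedy goes beyond normality.** It does, because it changes the contrast. That is justified by the mismatch in step 3.

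Two stronger readings are tempting, and the documents support neither. A reader might infer that the normality check is what costs the study its 8-point difference, and that the parametric branch would keep it. It would not, because that branch is also paired. A reader might also infer that the check will usually fail and often reverse the result, for example by testing raw cohort scores or by comparing a t-test with an unpaired rank-sum test. The written plan uses neither of those: a paired analysis turns on the distribution of the changes.

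**Conclusion.** The point holds in a limited form. The plan leaves the primary estimand to the observed distribution and names no effect estimate. Neither permitted test addresses the difference between cohorts on which the study was sized. The second defect is the larger one; the normality clause adds discretion that is unnecessary at 85 to 100 patients per group, where a comparison of means is robust. The clause should still go: making the tests unpaired while keeping it would leave the choice of quantity to the data.

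The stated sample size is adequate for the corrected contrast: about 0.82 to 0.84 power (t-based) for 8 points with SD 18. This rests on a two-sided test, 10–15% dropout and independent patients. As a rough allowance for clustering, take 4 patients per physiotherapist per phase and a design effect of 1 + 3 × ICC. An assumed ICC of 0.01 gives 83 evaluable, or 97 enrolled at 15% dropout. An ICC of 0.05 gives 92, or 109 enrolled. That formula treats the two phases as separate clusters. The same physiotherapists treat in both, so stable differences between them largely cancel, and baseline adjustment also reduces residual variance (by a factor of 1 − r², or 0.75 at an assumed r of 0.5). The documents give neither an ICC nor a correlation to settle the net effect.

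**What to change.** In the Statistics section, delete the bracketed clause that lets normality decide the test, and replace the paired comparison with one analysis per outcome, fixed in advance:

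- **Roland Morris disability (primary), pain, Örebro and work ability:** a linear model of the 3-month score on cohort (pre- or post-education) with the baseline score as covariate and standard errors clustered by treating physiotherapist. Report the mean difference with its 95% CI whatever the distribution.
- **7-point satisfaction item:** one named between-cohort method without baseline adjustment, since no baseline value is described. For the same reason the planned paired test has nothing to pair it with.
- **Rank-based or bootstrap analyses:** sensitivity analyses only. Within-patient change may be kept as description.

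The cost is small. Baseline and 3-month scores are already needed for the planned paired tests. The physiotherapist identifier is not among the listed baseline data, but recruitment is by physiotherapist, so it should be known and only has to be recorded. No additional patients are needed on the plan's own inputs, before any allowance for clustering. The change is more than wording in one respect: the primary contrast is restated as between cohorts, and this should be stated openly in an amendment.

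### Does the expected 30% group difference contradict the means of 36 and 28 used to size the study?

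*Combined protocol and SAP*

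**What the plan says.** The sample-size paragraph of the Statistics section describes the target effect twice. First it gives a relative figure taken from an earlier study in a similar population: "we expect to find a 30% group difference in disability in favor of the post-education group". It then gives the inputs: "With a mean of 36 (SD 18) pre-intervention and 28 (SD 18) post-intervention". From these it concludes that 100 per group is "sufficient to achieve an alpha level of 0.05 with a 0.8 power", after allowing for 10-15% dropout.

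The paragraph does not say what the 30% is a percentage of, whether alpha is one- or two-sided, or on which scale 36, 28 and 18 are measured. The primary outcome, listed under Procedures, is "Roland Morris Disability Questionnaire 3 months after entering the study".

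The two groups are separate patients. Under the schedule of procedures, 25 physiotherapists recruit 4 patients each before the course, and then "Point 1 is repeated on an additional 100 patients who undergo rehabilitation after the physiotherapists have completed the course".

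**The concern.** A reduction in favour of one group is normally expressed against the comparator, here the pre-education mean. On that base, 8 points out of 36 is 22%, well short of 30%. Two adjacent sentences then appear to give two target effects.

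If the 30% were the real input, the target would be 10.8 points and the required number of completers would be about half of what the means imply. If the percentage had driven the sample size, or if a later analysis judged success against it, the mismatch could leave the study wrongly sized or its result misread. So the question is whether anything in the plan rests on the percentage.

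**Working it through.** **Inputs (Statistics section, sample-size paragraph).** Means 36 and 28, SD 18 in both groups, alpha 0.05, power 0.80, dropout 10-15%, 100 per group. Two-sided testing is an assumption.

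**Step 1: the percentage.** The difference is 36 − 28 = 8 points.

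- Pre-education base: 8/36 = 22.2%.
- Post-education base: 8/28 = 28.6%.
- Midpoint base: 8/32 = 25.0%.

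**Step 2: can rounding explain it?** Assume that both means were rounded to whole numbers, so that they lie in 35.5-36.5 and 27.5-28.5. The difference is then between 35.5 − 28.5 = 7 and 36.5 − 27.5 = 9.

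- Pre-education base: 7/35.5 = 19.7% to 9/36.5 = 24.7%. This cannot reach 30%.
- Post-education base: 7/28.5 = 24.6% to 9/27.5 = 32.7%. This includes 30%.

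Put the other way, 28 × 1.30 = 36.4, which rounds to 36. The stated means therefore fit a 30% difference taken on the post-education mean.

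**Step 3: the plan's own sample size.** For two independent means, n per group = 2 × (1.960 + 0.842)² × (SD/difference)². With 8 points and SD 18, this is 2 × 7.85 × (18/8)² = 79.5, so 80. The exact t calculation gives 80.44, so 81.

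- Dropout 10%: 81/0.90 = 90 recruited.
- Dropout 15%: 81/0.85 = 95.3, so 96 recruited.

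The calculation does not return 100 exactly, but the plan says only that 100 is sufficient, and it is. With 90 or 85 of 100 retained, power is 0.843 or 0.821. The total also equals 25 physiotherapists × 4 patients.

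**Step 4: does any reading of the 30% raise the number?** Exact t, two-sided 0.05, power 0.80:

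| Target | Difference | Completers per group | Recruited at 10-15% dropout |
|---|---|---|---|
| Stated means | 8 | 81 | 90-96 |
| 30% of 28 | 8.4 | 74 | 83-88 |
| 30% of 36 (post-education mean 25.2) | 10.8 | 45 | 50-53 |

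The stated means are the most demanding of the three. If the test were one-sided, 8 points would need 64 completers, or 72-76 recruited.

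**Step 5: where else is the 30% used?** Nowhere. The analysis sentence of the Statistics section does not refer to it, and no outcome or success criterion is defined by it.

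**The case for a change.** The case for a change is that a sample-size statement should define one target effect, and this one can be read as 8, 8.4 or 10.8 points. A reader who starts from 30% of the pre-education mean arrives at 45 completers, not 81. The cited study cannot be consulted here, so it is open whether the percentage or the means is the figure carried over faithfully. The scale of 36, 28 and 18 is not named either, which makes the intended effect harder to recover. A sentence or two would settle all of this.

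Most of that is fair as a comment on the wording: the base is undefined, and on the usual base the percentage is wrong. But the means and SD are stated in full, so the calculation can be checked without the percentage. If the 30% were the true figure and a mean the slip, the study would need fewer patients. Writing down the base, the scale or the sidedness would alter no result.

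Two related matters do not depend on the percentage. The first is that the plan says "All primary and secondary outcomes will be analysed using paired tests (parametric or non-parametric based on normality", comparing baseline with 3 months, whereas the sizing compares two cohorts. The second is clustering: the same 25 physiotherapists treat 4 patients each in both periods. With an assumed intraclass correlation of 0.05, the design effect is 1 + 3 × 0.05 = 1.15. That gives 80 × 1.15 = 92 completers, or 103-109 recruited. Over assumed values of 0.01 to 0.10, the recruited number runs from 92-97 to 116-123. These figures ignore any precision gained from having the same physiotherapists in both periods. Both are separate questions, and correcting the 30% would answer neither.

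**Conclusion.** No change follows. The 30% is a loosely worded figure without a stated base. It conflicts with the means on the pre-education base (22%) and agrees with them within rounding on the post-education base (28.6%). The sample size rests on the 8-point difference and SD 18. For these, 100 per group gives power of 0.82 to 0.84 after 10-15% dropout, above the 0.80 claimed, and each alternative reading of the 30% needs fewer patients.

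This holds for a two-sided test at 0.05 comparing two groups of independent patients, with no allowance for clustering by physiotherapist. It also takes the stated means and SD at face value, since the source study and the scale cannot be checked from the document. It does not show that the sizing is adequate in every respect, only that the percentage does no harm to it.
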